Clinical Development

OMB157/Ofatumumab

COMB157G2102 / NCT03560739

**A 12 week randomized open label parallel group
multicenter study to evaluate bioequivalence of 20 mg
subcutaneous ofatumumab injected by pre-filled syringe or
autoinjector in adult RMS patients**

Statistical Analysis Plan (SAP)

Author:

[REDACTED] : [REDACTED]

Document type: SAP Documentation

Document status: Final 5.0 (Addendum 2)

Release date: 8-May-2020

[figure not shown]
[figure not shown]

[figure not shown]

Number of pages: 45

Property of Novartis
For business use only
May not be used, divulged, published or otherwise disclosed
without the consent of Novartis

Document History – Changes compared to previous final version of SAP

Date	Time point	Reason for update	Outcome for update	Section and title impacted (Current)
12-Sep-2018	FPFV	Creation of final version	N/A - First version	NA
07-Jun-2019	Prior to DBL	FDA feedback on submission; Align with submission planning and update for corrections and clarity	Amendment 1	
Section 2.3.5: Smoking and Alcohol history (removed summary tables as they are not needed)
 
Section 2.8.1: AEs (updated common AEs as $\geq 2\%$ per FDA feedback)
 
Section 2.8.2: Deaths (removed table summary as death is expected to be rare in this study)
 
Section 2.8.3: presentation of shift table for lab parameters are updated.
 
Section 2.8.3.2: Other lab parameters (added T-cell and minor corrections). 
 
Figure presentation for B-cell are updated.
 
Section 2.8.5: CSSRS (Added texts for “complete suicide” data collection per update of standard MAP); added data handling rules for all prior history and recent history if multiple assessments collected prior to first dose.
 
Section 2.4.2.1: Concomitant medication (added rules for cases with both missing start date and end date)
 
Section 2.4.2.3: Injection related premedication time window update

Date	Time point	Reason for update	Outcome for update	Section and title impacted (Current)
18-Sep-2019	Prior to DBL	Align with submission planning and update for corrections and clarity	Amendment 2	Section 2.4.1: Add condition of analysis cut-off date for time at risk definition. Section 2.1.2.1: [REDACTED] [REDACTED] to account for some assessments occurring outside the original definitions Sections 2.1.2.1, 2.8.3.2, 5.3.1: Remove left-over reference to T-cell assessment (T-cell analysis was already removed from previous amendment, due to panel unavailable at the study start) Section 2.3.5: Remove entirely (smoking and alcohol history information not needed in listings) Section 2.5.1: Clarify exclusion of concentrations / patients from BE analysis due to missing concentration value or dose missed due to reasons that are not protocol deviations (missed dose leads to the exclusion of two patients at the time of amendment). [REDACTED] Section 2.8.6: Final naming decision for Registration and Final CSR.

Date	Time point	Reason for update	Outcome for update	Section and title impacted (Current)
21- Oct- 2019	After DBL	Correct inaccurate reference to PD ID INCL01 and 	Addendum 1	
Section 4:  
 
Other minor corrections or clarifications made in the document.
 
Section 2.8.3.4: Other special lab results
 
Updates are made in order to provide more accurate information on 
  
2) correct the data cutoff for 
  
Same section: correction of error in explanation of notably low IgM/IgG criteria.
 
Section 5.6: Rule of exclusion criteria of analysis sets

Date	Time point	Reason for update	Outcome for update	Section and title impacted (Current)
				
Removed reference to protocol deviation ID INCL01 to prevent inappropriate exclusion of patients with this PD ID from analyses: At the time of writing of the SAP it was assumed that INCL01 would be assigned to PD “Informed consent obtained = 'No' or missing”, however, in the database no code was assigned to this deviation (and no patients affected), while INCL01 was in fact assigned to “Incorrect ICF procedure” as per Edit Check Specifications – which does not justify exclusion of patients from analysis. Impact: Change allows inclusion of data from two patients who consented, but were affected by incorrect ICF procedure in all analyses.
 
Document history: Correct date of amendment 2 to release date 18 Sep 2019 as provided on title page.

8- May- 2020	After DBL	Adapt plan for reporting of SFU patients to very low sample size	Addendum 2	
Section 2.1.2.1: Updated visit window definition for data after study drug discontinuation (replaced EOS date with Last dose date as starting point for visit window definitions).
 
Section 2.8.6.2: Clarify that only patients that did not roll over to the extension study or prematurely stopped treatment should be included in SFU analyses, to avoid contributions from patients not in SFU, who had unscheduled assessments shortly after the regular EOS/Week 12 visit.

Date	Time point	Reason for update	Outcome for update	Section and title impacted (Current)
				

Table of contents

Table of contents	7
List of abbreviations	9
Pharmacokinetic definitions and symbols	11
1 Introduction	12
1.1 Study design.....	12
1.2 Study objectives and endpoints	15
2 Statistical methods.....	15
2.1 Data analysis general information	15
2.1.1 General definitions	16
2.1.2 Visit windows.....	18
2.2 Analysis sets	20
2.2.1 Subgroup of interest	20
2.3 Patient disposition, demographics and other baseline characteristics	20
2.3.1 Patient disposition	20
2.3.2 Background and demographic characteristics.....	20
2.3.3 MS baseline disease characteristics	21
2.3.4 Medical history.....	21
2.4 Treatments (study treatment, rescue medication, concomitant therapies, compliance).....	21
2.4.1 Study treatment	21
2.4.2 Prior, concomitant and post therapies	22
2.5 Analysis of the primary objective.....	23
2.5.1 Primary endpoint.....	23
2.5.2 Statistical hypothesis, model, and method of analysis.....	24
2.5.3 Handling of missing values/censoring/discontinuations.....	25
2.5.4 Supportive analyses.....	25

PML	Progressive Multifocal Leukoencephalopathy
PRO	Patient-reported Outcomes

QTcF	QT correction formula
RBC	Red blood cells
RRMS	Relapsing-remitting Multiple Sclerosis
RSABE	Reference scaled average bioequivalence
SAE	Serious Adverse Event
SAP	Statistical Analysis Plan
sc	Subcutaneous
	
SIB	Suicidal ideation and behavior
SOC	System Organ Class
SPMS	Secondary progressive Multiple Sclerosis
TOST	Test one sided test
ULN	upper limit of normal
WBC	white blood cell(s)
WHO	World Health Organization

[figure not shown]
Pharmacokinetic definitions and symbols

AUC _{0-t}	The area under the plasma (or serum or blood) concentration-time curve from time zero to time 't' where t is a defined time point after administration (mass x time/volume)
AUC _{last}	The area under the plasma (or serum or blood) concentration-time curve from time zero to the time of the last quantifiable concentration (mass x time/volume)
AUC _{tau}	The area under the plasma (or serum or blood) concentration-time curve from time zero to the end of the dosing interval tau (mass x time/volume)
C _{max}	The observed maximum plasma (or serum or blood) concentration following drug administration (mass/volume)
T _{max}	The time to reach the maximum concentration after drug administration (time)

1 Introduction

The purpose of this Statistical Analysis Plan (SAP) is to describe the implementation of the statistical analysis planned in the protocol for study OMB157G2102 (G2102). The corresponding clinical study report (CSR) will include results from this SAP.

This document is consistent with the current study protocol (version 00).

1.1 Study design

This is a randomized, open-label, multi-center, parallel group 12-week study to evaluate the pharmacokinetic bioequivalence of ofatumumab injected by PFS or AI devices. The study design includes four parallel groups of RMS patients. Assessment of the primary and secondary endpoints are performed based on data collected through the dosing interval between Week 8 and Week 12 where approximate steady-state pharmacokinetics are anticipated.

Randomization: A total of approximately 150 eligible patients will receive open-label ofatumumab 20 mg sc every 4 weeks (after an initial loading regimen of three weekly 20 mg doses in the first 14 days). Patients will be randomized in a 5:5:1:1 ratio into the following 4 groups dependent on what type of injection device they will use and the location of their injection (62 subjects for groups 1 and 2, and 13 subjects for groups 3 and 4). Randomization will be stratified by body weight (< 60 kg, 60-90 kg, and > 90 kg) to ensure a balance between covariates with potential impact on the primary endpoint. Randomization will not be blinded as the endpoints of the study are primarily related to pharmacokinetics and all patients will be receiving active treatment at identical dosing regimens.

- Group 1: PFS, abdomen
- Group 2: AI, abdomen
- Group 3: PFS, thigh
- Group 4: AI, thigh

Interim analyses: The study will feature one interim analysis that will be conducted when approximately 36 patients have completed Week 12 ([Section 2.14](#)).

The study has 3 Parts:

- Part 1 – Screening
- Part 2 - Treatment
- Part 3 - Safety follow-up

Part 1 – Screening

[figure not shown]
- The Screening period can last up to 30 days and consists of Screening and Baseline assessments. Patient eligibility will be determined based on the Screening and/or Baseline assessments.

- Patients may be rescreened if they do not initially meet eligibility criteria. All assessments must be repeated, [REDACTED]

Part 2 – Treatment

Graphical outline of Part 2, Treatment period study design with four parallel groups. Evaluation of primary and secondary end-points are performed between Week 8 and Week 12.

Figure 1-1 Study design – Part 2

The study Part 2 Treatment period will consist of an initial induction phase (Week 0 to Week 4) and a pharmacokinetics phase (Week 8 to Week 12) at approximate steady-state conditions. Week 4 to Week 8 ensures that approximate steady-state conditions are reached prior to the pharmacokinetics phase. A schematic presentation of the study design is provided in [Figure 1-1](#).

The pharmacokinetics will be assessed for primary objectives during Week 8 to Week 12 at approximate steady-state conditions. The rationale for this is to avoid the expected larger inter-individual variation in exposure at treatment initiation due to the potentially different levels of

target expression between patients. This would result in high variability in the pharmacokinetics parameter leading to an increased sample size of the study. Further, the approximate steady-state condition is a clinically relevant situation as full target depletion would be expected in contrast to the situation after administration of a single dose typically used for bioequivalence assessment. During the study, ofatumumab will be administered to the respective groups of patients by a health care provider and according to specified instructions.

No clinically significant difference in ofatumumab exposure is expected between the two administration sites (abdomen vs thigh) (Xu et al 2010). Groups 3 and 4 will enable an assessment of the pharmacokinetics of ofatumumab injected to the thigh which can then be compared to abdominal administration using the PFS and AI, respectively. The aim of assessment of the injection site influence on ofatumumab pharmacokinetics is not to demonstrate bioequivalence but to enable an evaluation of the potential clinical significance of differences in pharmacokinetic parameters. Potentially, the absorption rate may vary between different injection sites for subcutaneous single dose administration of ofatumumab possibly resulting in different T_{max} and C_{max} values. However, under steady-state conditions and with the primary target being depletion of CD20-positive B-cells, the comparison of AUCs over the dosing period would be the most relevant parameter to evaluate. In order for patients to obtain a clinical benefit from participation in the study, continued treatment with ofatumumab will be offered to the eligible patients through enrollment into the umbrella open-label Phase 3 extension study (COMB157G2399). Patients waiting for open label extension study to open can continue to receive study drug. Patients should return every 12 weeks and complete assessments per assessment schedule.

Part 3 – Safety follow-up/Extension study

- The Safety FU period will be applicable for the following patients:
 - a. Patients who complete the Treatment period on study drug and do not enter the planned Extension study
 - b. Patients who prematurely discontinue study treatment
- All Safety FU visits must be scheduled relative to the EOS Visit.
- All patients will be followed for a total of at least 9 months after study drug discontinuation (by 9 months the vast majority of patients are expected to have repleted their circulating B-cells).

A longer than 9 months of post-treatment follow up in the Safety FU period will be required for patients who have not repleted their B-cells (ie B-cells not back to baseline value or to lower limit of normal (LLN) whichever comes first as determined by central lab) at 9 months. These patients will continue to be followed with 3-monthly assessments until their B-cell counts have repleted. Patients who have initiated therapy with another disease modifying/immunosuppressive therapy before the end of the 9-month follow up will not be monitored beyond 9 months.

1.2 Study objectives and endpoints

Table 1-1 Objectives and related endpoints

Objective(s)	Endpoint(s)
Primary Objective(s)	Endpoint(s) for primary objective(s)
To demonstrate pharmacokinetic bioequivalence of 20 mg ofatumumab injected by the PFS or AI devices	AUCtau Cmax
Secondary Objective(s)	Endpoint(s) for secondary objective(s)
To characterize the pharmacokinetics following subcutaneous administration of ofatumumab to either the abdominal region or the thigh	AUCtau Cmax
Assessment of immunogenicity	Proportion of patients with anti-ofatumumab antibodies
Assess the safety and tolerability of ofatumumab	Adverse events including injection related reaction, lab, vital signs, ECG, and eCSSRS

2 Statistical methods

2.1 Data analysis general information

Novartis statistical and programming team will be performing the final CSR analysis as planned in this document unless otherwise specified. The Statistical Analysis System (SAS) 9.4 and/or R 15.2.1 or higher versions will be used.

Unless otherwise stated, summary tables/figures/listings will be on all patients in the respective analysis sets. Categorical data will be presented as frequencies and percentages. For continuous data, mean, standard deviations, median, 25th and 75th percentiles (optional), minimum and maximum will be presented.

The Week 12 CSR analysis cut-off date will be the Week 12 visit date or EOS date if patients drop out of the study prematurely. All data up to this date will be included in the Week 12 CSR. A complete analysis of the post-treatment safety follow-up will be provided in the Final CSR when all patients have completed Safety FU period.

For analyses of adverse events, only data up to and including the safety cutoff of 100 days (5 x 20 days takes the long half-life of ofatumumab into account) after last administration of study drug or the subject entered the Study G2399 will be considered. Therefore, observations obtained more than 100 days after last administration of study drug will be excluded from the

analyses. Nevertheless, all serious adverse events (SAE) and all deaths, regardless of the safety cut-off will be summarized.

All data (collected or derived) will be listed appropriately.

Table 2-1 provides an overview on all planned reporting.

Table 2-1 Analyses for Week 12 registration vs. Final CSR

	Week 12 registration CSR	Final CSR
PK + immunogenicity	Complete	Complete
Tables + figures of planned safety assessments ¹	Complete up to Week 12 / EOS, no reporting of assessments during safety follow-up	Complete, including all assessments during safety follow-up
Listings of planned safety assessments ²	Complete up to 12 week DBL date	Complete, including all assessments during safety follow-up
Adverse events	Up to and including the safety cutoff of 100 days after last administration of study drug or the subject entered the Study G2399 or 12 week DBL date, whatever comes first	Up to and including the safety cutoff of 100 days after last administration of study drug or the subject entered the Study G2399, whatever comes first
Serious adverse events and deaths	Up to 12 week DBL date or subject entered the study G2399, whatever comes first	Up to final DBL date or subject entered the study G2399, whatever comes first

¹ These include also B-cells, total IgG, total IgM.

² These include also B-cells, total IgG, total IgM [REDACTED].

2.1.1 General definitions

Below summarize some general definitions to be used in the rest of the document.

Table 2-2 General definitions

Study treatment/Study drug	The investigational drug ofatumumab injected by PFS or AI devices will be referred as study treatment or study drug.
Date of first administration of study drug/first dose date	The first injection date of ofatumumab.
Date of last administration of study drug/last dose date	The last injection date of ofatumumab.
Study Day 1 or Day 1	The date of first administration of study drug/first dose date.

Study Day	
All other study days will be labeled relative to Day 1. For events with dates on or after Day 1, study day for the event is calculated as (event start date – first dose date + 1). For events with dates before Day 1, study day for the event is calculated as (event start date – first dose date).
 
Day 0 will not be used.

Duration of an event	Duration of an event is calculated as (event end date – event start date +1).
1 month	30 days; to be used in defining 3-month or 6-month confirmed disability worsening or improvement.
4 weeks	28 days; to be used in determining target days of scheduled visits. It is based on the scheduled injection frequency for ofatumumab (during the maintenance phase).
Day post-study drug discontinuation	Day post-study drug discontinuation for a particular event is calculated as (event start date – study drug discontinuation date).
Baseline	
Baseline is the last assessment obtained prior to the first administration of study drug. No visit windows will be needed for the identification of baseline assessment.
 
For pulse and blood pressure vital sign values, the baseline is the average of the non-missing values of the 3 measurements taken on the last visit prior to the first administration of study drug. The pre-injection assessment values on Day 1 vital sign CRF page will not be used for baseline derivations.

On-treatment period	On-treatment period includes days from the first injection date until 30 days after the last injection date; This definition considers patients are scheduled to inject every 28 +/- 3 days. The on-treatment definition applies to efficacy analyses only.
Safety cutoff (off-treatment)	Safety cutoff: Unless explicitly otherwise stated (e.g. SAEs and deaths), data up to and including the safety cutoff of 100 days after permanent study drug discontinuation will be included in the analysis and data beyond this time point for a given patient will be excluded from the safety analysis. The safety cutoff of 100 days (5x20 days) takes the long half-life of the investigational drug into account. The safety cutoff applies to safety analyses only.

Nominal visits	Nominal visits are defined as all scheduled visits as per the clinical study protocol including the EOS visits. The definition of nominal visit excludes unscheduled visits.
End of Study (EOS)	EOS, used in the context of individual patients, refers to EOS visit. EOS, used in the context of the entire study, refers to completion of Week 12 visit for all patients.
Last assessment on drug	It is the last assessment with non-missing value taken before or on the date of last administration of study drug. No visit windows will be needed for the identification of the last assessment on drug evaluation.

2.1.2 Visit windows

2.1.2.1 Visit windows definition

Visit-windows will be used for data summaries by visit/time point. Visit windows define a time period “around” the targeted visit date as defined in the evaluation schedule of the clinical study protocol. Visit-windows are non-overlapping, and defined without gaps between consecutive visit windows. The width of visit windows may vary over the course of the study period.

Baseline assessments are defined in [Section 2.1.1](#) and do not require a visit window.

The purpose of visit windows is to analyze data based on the actual study days (rather than "nominal" visits). E.g., if a patient’s Month 1 visit is delayed; it is possible that the Month 1 data be re-aligned to visit-window Month 2 and be summarized under Month 2.

- For **PK concentration** [REDACTED] nominal visits will be used for summaries by visit/time point. Due to the frequent sampling time points during week 8, conventional mapping to visit-windows are not considered appropriate, thus nominal visits are used in order to capture all data as intended.

-For **safety analyses** all visits (scheduled and unscheduled) will be mapped to visit windows. Safety data from unscheduled visits may be reported separately if applicable.

It is possible that more than one assessment of a patient fall into a particular visit-window. [Section 2.1.2.2](#) deals with the statistical approaches to handle multiple visits in a given visit-window.

Tables displaying summary statistics “by visit” will also use the term *visit-window* as column header; this is to remind the reviewer that multiple assessments of a patient might be summarized. Below tables provide visit-windows definitions for applicable parameters.

Table 2-3 Visit-windows for ADA

Visit-window	Start day	Target Day	End day
Week 4	1	28	42

Week 8	43	56	70
Week 12	71	84	97

Table 2-4 Visit-windows for routine laboratory values and IgG and IgM

Visit-window	Start day	Target Day	End day
Week 4	1	28	56
Week 12	57	84	111

Table 2-6 Visit-windows* for [REDACTED] vital signs data after study drug discontinuation

Visit-window	Start day	Target Day	End day
Last assessment on drug	NA	NA	NA (see above or Section 2.1.1)
Week 12 after LDD	2	84	126
Week 24 after LDD	127	168	210
Week 36 after LDD	211	252	294

*The Start day, Target day, and End day are relative to the LDD date. For the “Last assessment on drug”, the last assessment with non-missing value taken before or on the date of last administration of study drug will be summarized (no visit window applies). For the “Week 12 after LDD” visit-window, assessments taken at least 1 day after but no more than 126 days after the LDD date will be considered. LDD stands for last dose date and will be footnoted in applicable outputs.

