5.6.2 Discontinuation of study treatment

Discontinuation of study treatment for a patient occurs when study drug is stopped earlier than the protocol planned duration, and can be initiated by either the patient or the Investigator.

The Investigator must discontinue study treatment for a given patient if, on balance, he/she believes that continuation would negatively impact the risk/benefit of trial participation.

Discontinuation of study treatment does not mean discontinuation from study. The patient should return to the site as soon as possible, after discontinuation of study drug, for EOS visit. EOS visit assessments ([Table 6-1](#)) should be completed and results recorded in the CRF. The Investigator must determine the primary reason for the patient's premature discontinuation of study treatment and record this information on the appropriate CRF.

Study treatment must be permanently discontinued under the following circumstances:

- Patient wish (withdrawal of consent [Section 5.6.3](#))
- Pregnancy (see [Section 6.6.6](#) and [Section 7.6](#))
- Use of prohibited treatment ([Table 5-1](#))
- Diagnosis of PML
- Patient with active serious infections or reactivation (eg tuberculosis, hepatitis B or C)
- Skin and/or mucosal reactions which raise the suspicion of severe generalized major skin reactions (Stevens-Johnson syndrome, or toxic epidermal necrolysis-Lyell's syndrome)
- Hypersensitivity to the study medication
- Any situation in which study participation might result in a safety risk to the patient
- Protocol violation that results in a significant risk to the patient's safety
- Emergence of certain adverse events, such as malignancy (except successfully treated basal cell carcinoma, *in situ* squamous cell carcinoma and *in situ* carcinoma of cervix of uterus), liver failure or, serious chronic infection (such as HIV)

- Laboratory abnormalities (eg liver function tests (LFT)) and abnormal test procedure as defined in [Appendix 1](#)
- Severe hypoproteinemia
- Interstitial lung disease or new onset or worsening of pulmonary symptoms, such as persistent cough and dyspnea, with or without associated fever, suspicious of interstitial lung disease
- Non-compliance with study treatment

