Table 6-1 lists all of the assessments and indicates with an “x” when the visits are performed. Subjects must be seen for all visits on the designated day, or as close to it as possible. Missed or rescheduled visits should not lead to automatic discontinuation. In case a visit is performed outside the schedule, subsequent visits shall be performed in keeping with the original visit schedule. In addition to the scheduled visits, patients may have unplanned visits due to a MS relapse, an acute illness of undetermined cause, for other reasons, or at the discretion of the Investigator. Data collected during unplanned visits will be recorded in the unplanned visit CRFs. Patients who prematurely discontinue the study for any reason should be scheduled for a visit as soon as possible, at which time all of the assessments listed for the final visit will be performed. At this final visit, all dispensed investigational product should be reconciled and the adverse event and concomitant medications reconciled on the CRF.

Table 6-1 **Assessment schedule**

Period	Screening/Pretreatment		Induction					Pharmacokinetics							
	SCR D-30 to D-8	BL D-7 to D1	D1 ¹	D4	D7	D14	W4 D28	W6 D42	W8 D56	W8 D57	W8 D59	W9 D63	W10 D70	W11 D77	EOS ² / W12 D84
Visit															
Visit No.	1	20	110	120	130	140	150	160	170	180	190	200	210	220	1999
Visit Window (hours or days)	n.a.	n.a.	n.a.	±1d	±1d	±1d	±1d	±3d	±1d	±1d	±1d	±2d	±2d	±2d	±2d
HIV test	X														
eCSSRS	X ^{9a}	X ^{9a}	X	X	X	X	X	X	X	X	X	X	X	X	X
AEs	X	X	X	X	X	X	X	X	X	X	X	X	X	X	X
Prior/Con Meds ¹²	X	X	X	X	X	X	X	X	X	X	X	X	X	X	X
Study Disposition															X

1. Randomization and first dose (usually expected on the same day). If first dose occurs on a different day after randomization, the day of first dose should be considered to be Day 1. Patients must remain at the site under observation for a minimum of 5 hours following dosing on Day 1.
2. EOS visit will be required for all patients (Patients who permanently discontinue study drug and patients who complete the study). Patients waiting for open label extension study to open can continue to receive study drug. Patients should return every 12 Weeks and complete all EOS assessments with the exception of PK, [REDACTED] and ECG.

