6.2 Pharmacokinetics sampling

The primary objectives of this trial are depending upon the pharmacokinetics assessment of the study drug. Bioequivalence will be evaluated statistically based on AUC_{tau} and C_{max} values from individual patient time-concentration profiles of ofatumumab. Data from patients randomized to group 1 and 2 will be used for the bioequivalence assessment. Hence, it is of key importance that the dosing instructions, samples collection procedures and timing of visits during the study are followed closely. The dosing interval between Week 8 and Week 12 is of particular importance to obtaining accurately assessed bioequivalence data. Pharmacokinetics sampling has been scheduled prior to dosing on all dosing visits. The time window in which the respective visits should occur, is also specified in the assessment schedule (see [Table 6-1](#)). If, for some reason, the visit cannot be completed within the specified time window, the planned dose administration and associated blood sampling should still be carried out as close as possible to the originally planning time points. In all cases, the PK sample collection date and time must be recorded as instructed in the lab manual and entered in the appropriate CRF.

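### On the visible text, an early-discontinuation EOS sample is summarised as Week 12 in the descriptive PK concentration tables and plots, whatever the time since the last dose

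*SAP*

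**What the plan says.** **How PK concentrations are grouped.** SAP 2.1.2.1 maps safety data to study-day windows but exempts PK concentrations, for which "nominal visits will be used for summaries by visit/time point". The reason given is the dense sampling around the Week 8 dose. SAP 2.1.1 adds: "Nominal visits are defined as all scheduled visits as per the clinical study protocol including the EOS visits". Only unscheduled visits fall outside that definition.

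**EOS and Week 12 are one visit.** Protocol Table 6-1 has one column for EOS and Week 12 (target Day 84, ±2 days, visit number 1999). The SAP document history likewise speaks of the "regular EOS/Week 12 visit".

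**Who attends, and when.** Table 6-1, footnote 2: "EOS visit will be required for all patients (Patients who permanently discontinue study drug and patients who complete the study". Protocol 5.6.2: "The patient should return to the site as soon as possible, after discontinuation of study drug, for EOS visit". The introduction to Protocol Section 6 describes a prompt visit after premature discontinuation, "at which time all of the assessments listed for the final visit will be performed".

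**PK is among the EOS assessments, by implication.** Footnote 2 lifts PK only for patients waiting for the extension study, who "complete all EOS assessments with the exception of PK" and certain other items. For patients on schedule, Week 12 is a dosing visit (Protocol 6.7.2) and its sample is pre-dose: "Pharmacokinetics sampling has been scheduled prior to dosing on all dosing visits" (Protocol 6.2).

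**Where the values go.** SAP 2.7.2 summarises concentration by time point for all four arms on the PK analysis set. SAP 2.10 adds arithmetic and geometric means and plots.

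**What is excluded.** The PK analysis set (SAP 2.2, Table 5-6) drops only patients without consent or without a valid randomization number. The missed-dose exclusions (SAP 2.5.1; TRT06 in Table 5-5) apply to the bioequivalence analysis.

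**The concern.** A Week 12 value should be the concentration about 28 days after the Week 8 dose. Under the nominal-visit rule, the row with that label can also hold a sample taken a few days after a dose (a patient who stopped early and came straight to EOS). It can likewise hold one taken about 56 days after a dose (a patient who missed Week 8 but attended Week 12). The first inflates the Week 12 mean and the second deflates it, so the errors cannot be assumed to cancel.

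The SAP's reason for using nominal visits does not extend to this sample, whose nearest scheduled neighbour is a week earlier. ADA and routine laboratory values are windowed by study day (SAP Tables 2-3 and 2-4), so an early EOS value there moves to its own window. PK concentration, which depends most directly on time since dose, has no such rule in the visible text.

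At stake is one row of a descriptive table and one plotted point per arm. The thigh arms, with 13 patients each, are the most exposed.

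**Working it through.** **1. The plan's own figures.** Dropout is 3% (SAP 3.1, 3.2). Per arm, 60/0.97 = 61.9, rounded up to 62, and 12/0.97 = 12.4, rounded up to 13. Both match. The stated 90% CI width for thigh versus abdomen is 0.78. With σ = √ln(1 + 0.85²) = 0.737, the width is 2 × t(0.95, 70) × 0.737 × √(1/60 + 1/12) = 0.777, which also matches.

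**2. How often.** P(at least one early discontinuer) is 1 − 0.97^13 = 0.33 in a thigh arm and 1 − 0.97^62 = 0.85 in an abdomen arm. Not every dropout will give an EOS sample, so for early stoppers these are upper figures. Patients who miss Week 8 but stay in the study come on top. The SAP document history (Amendment 2) mentions two patients excluded from the bioequivalence analysis for a missed dose, but gives neither arm nor visit.

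**3. Simple size.** Assume a 20-day half-life, mono-exponential decline and the same level just after each dose. The 20 days is the figure implied by the 100-day safety cutoff (5 × 20, SAP 2.1), not a PK estimate.
- Sample 7 days after a dose, relative to the 28-day trough: 2^(21/20) = 2.07.
- One of 13, geometric mean: 2.07^(1/13) = 1.058, or +5.8%.
- One of 13, arithmetic mean: (12 + 2.07)/13 = 1.082, or +8.2%.
- Two of 62, geometric mean: 2.07^(2/62) = 1.024, or +2.4%.
- Sample 56 days after the last dose: 2^(−28/20) = 0.38. One of 13 gives 0.38^(1/13) = 0.93 (−7%) and (12 + 0.38)/13 = 0.95 (−5%).

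**4. Range over the half-life.** This uses one-compartment superposition of doses on Days 1, 7, 14, 28 and 56, with absorption rate 0.25 to 0.5 per day and EOS on selected days from Day 4 to Day 77. All of these except the dose days are assumptions.

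| Half-life | EOS sample ÷ Day 84 trough | 1 of 13, geometric | 1 of 13, arithmetic | 2 of 62, geometric | 2 of 62, arithmetic |
|---|---|---|---|---|---|
| 20 days | 0.58 to 2.67 | −4% to +8% | −3% to +13% | −2% to +3% | −1% to +5% |
| 10 days | 1.60 to 7.74 | +4% to +17% | +5% to +52% | +2% to +7% | +2% to +22% |
| 5 days | 2.50 to 35.35 | +7% to +32% | +12% to +264% | +3% to +12% | +5% to +111% |

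**5. Against sampling error.** Assume the planned 85% CV also holds for troughs; the documents give no trough CV. The log-scale SE is 0.737/√13 = 0.20 in a thigh arm and 0.737/√62 = 0.094 in an abdomen arm. The shifts in step 3 are ln(1.058) = 0.056 and ln(1.024) = 0.024, each about a quarter of one SE. The thigh shift is also about one-seventh of the accepted CI half-width (0.056 against 0.39). With a 10-day half-life the largest thigh shift is ln(1.17) = 0.157, about 0.8 SE.

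**The case against.** **Consequence.** The case for leaving the rule alone is that little hangs on it. The objective on injection site has AUCtau and Cmax as endpoints, and Protocol 3.1 names AUC over the dosing period as the most relevant parameter. Concentration by time point is purely descriptive, few patients are involved, and the shift at a 20-day half-life is well inside sampling error. Actual sampling times are recorded and all data are listed, so an off-time value can be found. All of this stands and sets the severity. It does not make the Week 12 label correct.

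**Hidden text.** A redaction sits inside the sentence that sets the rule. The Amendment 2 log entry for the same section is partly blacked out, Table 2-5 is not visible, and neither is the PK row of Table 6-1. A separating rule may exist, or PK at an early EOS may be handled differently. That limits confidence.

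**Flagging.** SAP 2.5.1 allows missing or below-LOQ values to be flagged out of data presentations generally, not only out of the bioequivalence analysis. A measurable sample taken at the wrong time is neither, so this does not resolve the point.

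**Stronger readings that a reader might infer.**
- That the bioequivalence result is contaminated. The documents do not support this: the nominal-visit rule governs summaries by time point, the test uses each patient's AUCtau and Cmax from the Week 8 interval, and patients with a missed dose are removed from it.
- That the Week 12 trough is used to test injection sites or to confirm steady state against Week 8. Neither document plans such a comparison, and no formal testing is planned for the thigh arms.

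**Conclusion.** The point holds as a minor one, with medium confidence. Followed literally, the visible rules place EOS samples from early discontinuers, and Week 12 samples after a missed Week 8 dose, in the Week 12 concentration summaries without regard to time since dose. The effect is confined to the descriptive output of SAP 2.7.2 and 2.10.

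One such patient in a 13-patient thigh arm moves the geometric mean by roughly 6% upward (7 days after a dose) or 7% downward (56 days). The effect in an abdomen arm is smaller. These figures rest on the assumed 20-day half-life and mono-exponential decline; a shorter half-life makes the upward shift larger. The chance that a given thigh arm has any early discontinuer is about one in three at the planned dropout rate.

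**What to change.** Keep nominal visits for PK in SAP 2.1.2.1, and add that a visit-1999 PK sample counts as Week 12 only if both conditions hold:
1. the Week 8 dose was given;
2. the visit is the patient's Week 12 visit rather than an early-discontinuation EOS, judged by actual time since the Week 8 dose: 28 days, with one tolerance stated in advance.

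List every other EOS sample by actual time since last dose, and leave it out of the Week 12 summaries, means and plots in SAP 2.7.2 and 2.10.

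The rule should be anchored to the Week 8 dose and not to Day 84 ± 2. If the ±3 days for maintenance doses in Protocol 5.5.4 is read around planned Day 56, a sample inside the Day 84 window can lie 28 − 3 − 2 = 23 to 28 + 3 + 2 = 33 days after that dose. A tolerance below 5 days could then discard visits that met both windows. Some further room is needed for completers' slightly late visits, which Protocol 6.2 says should still be carried out and sampled.

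The cost is a short addition to the SAP and one programming condition. The downside is that a few samples move from a summary to a listing. If the redacted text already contains such a rule, nothing more is needed than to confirm that it covers both kinds of sample.
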